6.4.3 Secondary Analyses

No secondary analyses are planned.

6.4.4 Safety Analyses

Safety analyses will be based on the Safety Analysis Set, defined in section 3.3.

The number and percentage of subjects experiencing Pre-treatment AE (PTAEs) will be summarized by treatment, MedDRA system organ class and preferred term. This information will also be presented for the most commonly reported adverse events ($\geq 5\%$ in one or more treatment groups). PTAE is defined as any AE present prior to the initiation of the IP usage.

The number of subjects with PTAEs will be summarized by severity (mild, moderate and severe) for all adverse events. Subjects will be counted only once for each system organ class and preferred term by selecting the most severe event.

The number and percentage of subjects experiencing treatment-emergent AEs will be summarized by treatment, MedDRA system organ class and preferred term.

The number and percentage of subjects experiencing treatment-emergent AEs will also be summarized by treatment, MedDRA system organ class, preferred term and severity. Subjects will be counted only once for each system organ class and preferred term by selecting the most severe event.

The number and percentage of subjects experiencing treatment-related AEs will be summarized by treatment, MedDRA system organ class, and preferred term. Treatment-related AEs are events evaluated by the investigator as being possible, probable or very likely related to study products. AEs with an unknown relationship to treatment will be considered to be treatment-related.

[figure not shown]
The number and percentage of subjects experiencing treatment-related AEs will also be summarized by treatment, MedDRA system organ class, preferred term and severity.

The number and percentage of subjects who discontinued the study due to adverse events (based on study disposition) and the number and percentage of subjects experiencing serious adverse events will be summarized by treatment. These displays will include all AEs.

Listings of all adverse events will be provided. Treatment-emergent AEs and PTAEs, if present, will be listed separately.

[REDACTED]

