### 8.3. [REDACTED] Safety Analysis

[REDACTED]

The safety analysis will be based on all randomized subjects who use IP. The number and percentage of subjects experiencing AEs during the clinical study will be presented by MedDRA System Organ Class, preferred term, and treatment. A listing of AEs will be provided for all subjects who signed the ICD, differentiating Pre-Treatment Adverse Events.

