APPENDIX 2 SUMMARY TABLES

Disposition of subjects:

- Study completion status and subject evaluation

Demography and Baseline characteristics:

- Demographic and baseline characteristics, Fitzpatrick Skin Type
- Skin Type – Oiliness Level at Screening rated by subjects.

Efficacy variables:

- Fitzpatrick Wrinkle and Elastosis Scale. Analysis of the primary efficacy variable will be based on the average scores as well separately for the scores from each Expert Grader.
- Modified Griffiths Scale

■ [REDACTED]

■ [REDACTED]

Adverse events [REDACTED]:

- Summary of Adverse Events
- Summary of Treatment-Emergent Adverse Events by System Organ Class and Preferred Term
- Summary of Commonly Reported Adverse Events
- Summary of Treatment-Emergent Adverse Events by System Organ Class, Preferred Term and Severity
- Summary of Treatment Related Adverse Events by System Organ Class and Preferred Term
- Summary of Treatment Related Adverse Events by System Organ Class, Preferred Term and Severity
- Summary of Pre-Treatment Adverse Events by System Organ Class and Preferred Term
- Summary of Pre-Treatment Adverse Events by System Organ Class, Preferred Term and Severity
- Summary of Adverse Events that Resulted in Study Discontinuation
- Summary of Serious Adverse Events

■ [REDACTED]

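### SAP 6.4.4 ties the ≥5% common-AE table to pre-treatment events and sets no onset limit on the SAE and AE-discontinuation displays (minor; correct the wording)

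*SAP*

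**What the plan says.** The second paragraph of SAP 6.4.4 deals with PTAEs throughout. It opens: "The number and percentage of subjects experiencing Pre-treatment AE (PTAEs) will be summarized by treatment, MedDRA system organ class and preferred term". The next sentence is the common-event rule, "This information will also be presented for the most commonly reported adverse events", with the 5% threshold in brackets. The paragraph closes with the definition: "PTAE is defined as any AE present prior to the initiation of the IP usage".

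The treatment-emergent summary comes two paragraphs later: "The number and percentage of subjects experiencing treatment-emergent AEs will be summarized by treatment, MedDRA system organ class and preferred term". A version by severity follows it. Neither mentions a 5% cut.

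Near the end of 6.4.4, discontinuations due to AEs are summarized by treatment, and "the number and percentage of subjects experiencing serious adverse events will be summarized by treatment. These displays will include all AEs".

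SAP Appendix 2 lists a "Summary of Commonly Reported Adverse Events" with no statement of which events it covers. The entries directly before and after it are both treatment-emergent tables. The SAE and AE-discontinuation titles also carry no qualifier.

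In the protocol, section 8.3 uses the phrase "differentiating Pre-Treatment Adverse Events" for the listing of AEs. Section 8.1 uses the same words for how AEs will be summarized.

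**The concern.** A programmer working from 6.4.4 alone would build the common-event table from PTAEs. Those events arise while both cells use the same cleanser and moisturizer and neither uses a mask, so the table would say nothing about the mask. A programmer working from Appendix 2 would probably build it from treatment-emergent events. A third could pool everything. The plan does not settle which.

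The SAE and AE-discontinuation displays raise a narrower form of the same problem. AEs are captured from consent (SAP 4.2; Protocol 10.3.3), so events before the mask are in the data. The Safety Analysis Set (SAP 3.3) selects women who used the product; it does not select events by onset. Counts in these two displays are likely to be small, so one misplaced event would be visible.

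What is at stake is whether three by-arm displays show what a reader will take them to show. Tolerability against sham is part of the stated objective, and these are displays a reader would consult on it.

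**Working it through.** The plan gives no figure to reproduce on this point. The check is a reading of the text, followed by an illustration of size.

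**Text, side by side**

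| Display | SAP 6.4.4 | Appendix 2 title | Events covered |
|---|---|---|---|
| Common AEs (≥5%) | Second sentence of the PTAE paragraph | Unqualified, between two treatment-emergent tables | PTAEs by 6.4.4; probably treatment-emergent by Appendix 2 order |
| SAEs | By treatment, all AEs | Unqualified | Any onset from consent |
| AE discontinuations | By treatment, all AEs | Unqualified | Any onset of the causing AE |
| AEs by class/term, and with severity | Treatment-emergent | Treatment-Emergent | After mask start |

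1. In the 5% sentence, the opening words refer back to the preceding sentence, which is the PTAE summary. The next sentence defines PTAE. No other sentence states a 5% rule.
2. The SAE and discontinuation sentence sets no onset limit. If it only means regardless of causality, there is still no onset limit.
3. The Safety Analysis Set excludes women who never used the mask. Every discontinuation counted in that set therefore happened after mask use began, and only the causing AE can have begun earlier. For an SAE, the only route is a serious event before first use in a woman who then starts the mask.

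**Size of the window**

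Screening is up to 10 days before Baseline, and a split Visit 2 can add 3 days (Protocol 7.1). If both visits fall on one day the screening interval is zero. Ten days is 10/(10 + 84) = 10.6% of the time to Week 12, and 10/(10 + 168) = 5.6% of the time to Week 24.

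**Illustration of the common-event table**

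- Per cell: 48 completers are targeted. About 125 enrolled and split evenly, which is assumed, gives about 62.
- Threshold k: 0.05 × 48 = 2.4, so 3 women; 0.05 × 60 = 3; 0.05 × 62 = 3.1, so 4. Hence k = 3 for n = 48 to 60 and k = 4 for n = 61 or 62.
- Weekly rate h of a given term: **assumed**, equal in both cells, 0.5% or 1%. The documents give no rate.
- Risk over d days: p = 1 − exp(−h·d/7). With h = 0.005, d = 10 gives 0.71%, d = 13 gives 0.92%, and d = 84 gives 5.8%.
- Chance that at least one cell reaches the threshold: 1 − (1 − P[Bin(n, p) ≥ k])².

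For example, at n = 48 over 10 days P[Bin ≥ 3] = 0.0049, so 1 − 0.9951² = 1.0%. Over 84 days P[Bin ≥ 3] = 0.535, so 1 − 0.465² = 78%.

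| h per week | n per cell | PTAEs, 10 days | PTAEs, 13 days | 12 treatment weeks |
|---|---|---|---|---|
| 0.5% | 48 | 1.0% | 2.0% | 78% |
| 0.5% | 60 | 1.8% | 3.6% | 90% |
| 0.5% | 61-62 | 0.2% | 0.5% | 73-74% |
| 1% | 48 | 6.1% | 11% | over 99% |
| 1% | 60 | 10.5% | 19% | over 99% |

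The contrast comes from 10 to 13 days against 12 weeks and does not depend on the exact rate. It describes how often a row appears in one table. It does not describe any change in a safety conclusion.

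**The case against.** The strongest reply is that this is one misplaced sentence with little consequence. Both neighbours of the common-event table in Appendix 2 are treatment-emergent tables, and the sentence speaks of adverse events, not PTAEs. A ≥5% treatment-emergent table would only be a filtered subset of the full class-and-term table already planned. That stands, and it is why the point is minor. It does not remove the conflict, because no text limits the table to treatment-emergent events.

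A second reply is that "These displays will include all AEs" follows the treatment-related tables and naturally means regardless of relationship. Reporting every SAE is also a defensible choice. That may well be the intent, but the displays would still mix events from before and after mask start without marking them.

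A third is that the Safety Analysis Set and the short window leave few ways in for an early event. This stands and narrows the SAE and discontinuation part considerably.

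A reader might infer a breach of Protocol 8.3. The documents do not support that: the differentiation in 8.3 concerns the listing, and the SAP lists treatment-emergent AEs and PTAEs separately. Protocol 8.1, which speaks of summaries, is the relevant text. The SAP's separate PTAE tables partly meet it; these three displays do not.

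**Conclusion.** The point holds as a minor correction. As written, SAP 6.4.4 yields a by-arm common-event table of pre-mask events only, in conflict with the order of Appendix 2. The by-arm SAE and AE-discontinuation displays do not distinguish an AE that began before first mask use in a woman who later used the mask, although Protocol 8.1 says summaries will make that distinction.

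A reader might go further and infer that the comparison of tolerability with sham is lost, or that no safety table isolates events after mask start. The documents do not support this. By-arm treatment-emergent tables by class and term, and by severity, are planned, and the listings are separate. Some safety content is also redacted and cannot be assumed absent. Nor do the calculations show that any safety conclusion would change.

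The textual finding rests on the wording alone. The probabilities rest on assumed weekly rates, equal in both cells, and on an even split. A further gap bears on the repair: neither document defines treatment-emergent, which can only be inferred as the opposite of PTAE.

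**What to change.** - In SAP 6.4.4, move the 5% sentence to follow the treatment-emergent summary by class and term (or repeat it there), and limit it to treatment-emergent AEs.
- Retitle the Appendix 2 table *Summary of Commonly Reported Treatment-Emergent Adverse Events*.
- State that the SAE and AE-discontinuation displays include events whatever their relationship to treatment, with PTAEs shown separately from treatment-emergent AEs.
- Define a treatment-emergent AE as the complement of a PTAE: an AE not present before the first use of the investigational product.

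The cost is a few SAP wording edits, an onset filter in the table programs, and one extra row or column in two displays. No new data are needed, and the planned PTAE tables still report the earlier events.

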## **3. STUDY DESIGN**

This is a single-center, 2-cell, sham-controlled, randomized, evaluator-blinded clinical usage study utilizing three Expert Graders (i.e. the PI plus two additional board-certified dermatologist Expert Graders; see Appendix XI). Up to approximately 125 subjects will be enrolled to finish with at least 96 subjects (targeting 48 subjects per cell). The target population is 35- to 70-year-old females with mild to moderate mottled hyperpigmentation on the face and moderate to severe facial wrinkles. Enrollment will be evenly distributed across all Fitzpatrick skin types (i.e. an approximately equal number of subjects will be enrolled per skin type per cell).

Subjects will be assessed at Screening, Baseline (Week 0), Week 1, Week 4, Week 12, and Week 24, as described in section 7.

At Screening (Visit 1), each subject will be provided with an auxiliary cleanser (twice daily usage – morning and evening) and an auxiliary moisturizer (once daily usage in the morning after cleansing [plus additional evening usage (after completing the mask treatment, as applicable), as desired]) to use full-face for the duration of the study. At Baseline (Visit 2), each subject will be randomly assigned to also use either the

active or sham light therapy mask (with respective activator; once daily usage for 10 minutes in the evening after cleansing) for the 12-week treatment period of the study. The active and sham masks will be identical in appearance; the Expert Graders will be blind to the IP assignment, and subjects will also be blinded to the extent possible (see section 6.6).

A 12-week regression period will begin at Week 12 (Visit 5); during the regression period, subjects will continue using the auxiliary products as described previously, but there will be no mask usage.

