## **7. INVESTIGATIONAL PLAN**

### **7.1. STUDY DURATION**

The study will consist of 6 visits\* over 24 weeks with visits scheduled at Screening (Visit 1\*\*), Baseline (Week 0; Visit 2), Week 1 (Visit 3), Week 4 (Visit 4), Week 12 (Visit 5), and Week 24 (Visit 6). Baseline to Week 12 (Visit 2 to Visit 5) will comprise a 12-week treatment period, and Week 12 to Week 24 (Visit 5 to Visit 6) will comprise a 12-week regression period.

As necessary, Visit 3 may be adjusted  $\pm$  2 days and Visits 4-6 may be adjusted  $\pm$  3 days. All scheduling windows are versus the Baseline visit (Visit 2 or [if applicable] the final Visit 2 sub-visit, as described below).

\*If required based on Expert Grader availability, Visits 2-6 may each be separated into up to three sub-visits. In such cases, each sub-visit will be identified by the suffix -A, -B, or -C (e.g. Visit 2A, 2B, and 2C); the date and procedures for that sub-visit will be clearly recorded in the source documentation, and all sub-visits for a particular time point should still occur within the prescribed scheduling window. Imaging and the subject questionnaire may be conducted at one sub-visit, while the clinical and subjective evaluations of efficacy and tolerance may occur at (a) separate sub-visit or sub-visits (before or after the imaging visit, as needed). The subject acclimation and interviews for AEs, compliance, and changes in health/medications will be conducted at each sub-visit. If Baseline (Week 0, Visit 2) is split, the sub-visits will occur within 3 days of one another (e.g. if Visit 2A is on a Monday, the final sub-visit will be completed by Thursday), and subjects will be instructed not to begin IP usage until the final sub-visit is complete. If Visit 5 is split, subjects will be instructed to continue the treatment period instructions until the final sub-visit is complete (i.e. IP will be collected and the regression period will begin at the final Visit 5 sub-visit). If Visit 6 is split, subjects will be instructed to continue the regression period instructions until the final sub-visit is complete (i.e. auxiliary products will be collected at the final Visit 6 sub-visit). The Site will use the fewest sub-visits possible.

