### **10.3.3. Procedures for Reporting AEs**

All AEs will be reported from the time a signed and dated ICD is obtained until completion of the subject's last study procedure or visit (or termination if the subject terminates early from the study for any reason).

AEs that occur within 30 calendar days after completion of the study will only be reported to the Sponsor if they are serious (i.e. SAEs). SAEs are reportable beyond this period if the event is considered study-related. The Sponsor will evaluate any safety information that is spontaneously reported by the PI/Site beyond this time frame.

Subjects are encouraged to report AEs spontaneously and in response to questioning during the visit (e.g. if they have had any side effects/issues or changes in their health since their last appointment). For each AE reported by the subject or observed by the Site team, the Site team member should notify the PI or designee, who will collect information about the event.

All AEs, regardless of seriousness, severity, or presumed relationship to study procedures, must be recorded using medical terminology. Whenever possible, diagnoses should be given when signs and symptoms are due to a common etiology (e.g., cough, runny nose, sneezing, sore throat, and head congestion should be reported as “upper respiratory infection”). The PI (or medically qualified designee) must record or confirm their opinion concerning the seriousness, severity, and relationship of the AE to the study. All measures required for AE management must be recorded and reported according to Sponsor instructions.

These events must then be entered into the EDC system within 3 business days of the site’s awareness.

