1 INTRODUCTION

1.1 STUDY OBJECTIVES

As stated in the protocol:

The objective of this study is to evaluate the efficacy and tolerability of an investigational light therapy mask in comparison to a sham mask device over a 12-week usage period and after a 12-week regression period for subjects with mild to moderate mottled hyperpigmentation and moderate to severe facial wrinkles.

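### No visible AE table separates the 12 mask weeks from the 12 off-mask weeks, and the treatment-emergent window has no stated end

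*SAP*

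**What the plan says.** The objective, in SAP 1.1 and Protocol section 2, is to evaluate efficacy and tolerability against sham "over a 12-week usage period and after a 12-week regression period". Protocol 7.1 fixes the first half: "Baseline to Week 12 (Visit 2 to Visit 5) will comprise a 12-week treatment period". For the second half, the same section of the protocol says: "Week 12 to Week 24 (Visit 5 to Visit 6) will comprise a 12-week regression period". In that second half, according to Protocol section 3, "subjects will continue using the auxiliary products as described previously, but there will be no mask usage". All masks and activators are collected at Visit 5 (Protocol 7.2.4).

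AE collection does not stop there. The rule in Protocol 10.3.3 begins "All AEs will be reported from the time a signed and dated ICD is obtained until completion of the" and closes the window at each person's final procedure or visit, which is Week 24 for a completer. Protocol 8.3 then plans: "The number and percentage of subjects experiencing AEs during the clinical study will be presented by MedDRA System Organ Class, preferred term, and treatment". SAP 6.4.4 has the corresponding table: "The number and percentage of subjects experiencing treatment-emergent AEs will be summarized by treatment, MedDRA system organ class and preferred term". Both use the same safety set, namely randomized subjects who used the product.

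The only time boundary in the AE analysis is the start of mask use: "PTAE is defined as any AE present prior to the initiation of the IP usage". SAP 6.4.4 and Appendix 2 also plan treatment-related, severity, serious and discontinuation summaries. None of those that can be read is split at Week 12 or at last mask use.

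**The concern.** The objective asks two tolerability questions, one for the period of use and one for the period after it. Efficacy is analysed at Weeks 1, 4, 12 and 24, so it can address each. The visible AE tables give one post-baseline figure per arm and address neither separately. In the all-events table, a headache in Week 20 carries the same weight as one in Week 2.

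For event types that people have anyway, the off-mask weeks add background events to both arms and no mask effect. A real on-mask excess is then harder to see, in a trial with about 48 completers per arm. The tables also cannot show whether an excess of AEs was confined to the weeks of use.

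**Working it through.** **Plan's own figures.** The documents give no AE rate and no safety power. The one calculated figure is the 92% efficacy power in Protocol 8.4. It reproduces at 92.4% (noncentral t, 48 per arm, 0.7 read as a standardized effect, two-sided 0.05) but has no bearing here.

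**Inputs from the documents.** Treatment period 12 weeks and regression period 12 weeks (Protocol 7.1). No mask use in the second (Protocol section 3). AE collection to the last visit (Protocol 10.3.3). Percentages over a fixed set of subjects (SAP 3.3).

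**Assumptions.** Background risk *b* per 12 weeks, the same in both arms and in both periods. Extra risk *x* from the active mask in Weeks 0 to 12 only. All risks independent.

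**Formulas.**
- On-mask: active = 1 − (1−b)(1−x); sham = b.
- Pooled to Week 24: active = 1 − (1−b)²(1−x); sham = 1 − (1−b)².
- Risk difference: on-mask = x(1−b); pooled = x(1−b)². Pooling therefore multiplies it by (1−b).

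**Worked case, b = x = 10%.** On-mask: 1 − 0.9 × 0.9 = 19.0% against 10.0%. Pooled: 1 − 0.81 × 0.9 = 27.1% against 1 − 0.81 = 19.0%. Ratio: 19.0/10.0 = 1.90, then 27.1/19.0 = 1.43. Difference: 9.0, then 8.1 points.

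**Range, x = 10%.**

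| b | On-mask, active v sham | Pooled, active v sham | Risk ratio | Risk difference (points) |
|---|---|---|---|---|
| 0% | 10.0% v 0% | 10.0% v 0% | undefined | 10.0 → 10.0 |
| 5% | 14.5% v 5.0% | 18.8% v 9.8% | 2.90 → 1.93 | 9.5 → 9.0 |
| 10% | 19.0% v 10.0% | 27.1% v 19.0% | 1.90 → 1.43 | 9.0 → 8.1 |
| 20% | 28.0% v 20.0% | 42.4% v 36.0% | 1.40 → 1.18 | 8.0 → 6.4 |

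**Visibility of a larger effect, x = 20%, 48 per arm.** For a two-sided 0.05 comparison of two proportions, power falls from 62% to 43% at b = 10%, and from 41% to 24% at b = 20%. No between-arm AE test is visible in the plan, so these figures only indicate how easily an excess would be noticed.

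**Do the treatment-related tables remove the off-mask events?** Only in part. SAP 6.4.4 takes relatedness to study products in general and counts an unknown relationship as related. Protocol 10.3.2.4 grades relatedness to study participation. The cleanser and SPF 30 moisturizer continue to Week 24, so a moisturizer reaction in Week 20 can sit in the same cell as a mask reaction in Week 2. In the severity tables a subject is counted once per term at the worst grade, so a severe off-mask event can displace a mild on-mask one.

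**The case against.** The strongest reply is that little is lost, and much of it stands.

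- A reader might infer that all mask toxicity is diluted. It is not. The tables give percentages over a fixed denominator, so extra weeks cannot remove a subject already counted, and a purely mask-specific event keeps its contrast in full (first row of the table). A true halving would need an exposure-adjusted rate (12 of 24 weeks), and none is planned.
- The ratio is the least favourable metric. On the difference scale the loss is 10% of the effect at b = 10%. The reported active-arm percentage actually rises, from 19.0% to 27.1%, so the mask looks better only relative to sham.
- A reader might infer that tolerability after stopping goes unanalysed. The documents do not support that. Protocol 7.1 refers to evaluations of tolerance, the schedule in Table 2 places the clinical and subjective evaluations at Visits 2 to 6, and Protocol 10.3.2.1 treats irritation signs as a clinical endpoint. Safety text in Protocol 8.3 and in the SAP is redacted and may contain by-visit analyses.
- Causality grading takes timing into account, so many late background events should drop out of the treatment-related tables. This is real but partial mitigation, for the reasons in the working.
- AE dates are collected and all events are listed, so a reader with the listings could separate the periods by hand. No visible decision rule depends on these tables.

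What remains is that the visible AE summaries do not match the two-part objective, and the term that defines their window has no end.

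**Conclusion.** The point holds as a gap in definition and presentation. No data are lost and the primary endpoint is untouched. Pooling to Week 24 is the natural reading of Protocol 8.3 with an undefined treatment-emergent window; the SAP does not state it as a rule. The effect is limited to events that also occur without the mask. There the risk difference shrinks by the factor (1−b), and the risk ratio moves further: from 1.90 to 1.43 at b = x = 10%, and from 1.40 to 1.18 at b = 20%. These sizes rest on assumed rates, a constant background and independence between periods, none of which the documents supply.

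A reader might go further and conclude that the on-mask period should be the main tolerability result. The documents do not support that ranking, because the objective names the time after regression as well.

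**What to change.** In SAP 6.4.4, define treatment-emergent with both a start (first mask use) and an explicit end. In SAP 6.4.4 and Appendix 2, present the treatment-emergent, treatment-related and severity tables by AE onset date for (1) first to last mask use and (2) after last mask use to Week 24. Keep the overall column so that delayed events stay visible. State the denominator for each period, since subjects who leave early contribute little or nothing to the second. Settle this before database release, so that the window is not chosen after the results are seen.

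The data exist: occurrence dates are collected for every AE (Protocol synopsis), and the daily diary and activator counters document mask use (Protocol 7.3). The cost is SAP wording and a few extra columns with smaller counts per period. Trial conduct does not change.
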